13.1.2 Serious Adverse Reaction/Event

An adverse event or suspected adverse reaction is considered "serious" if, in the view of either the investigator or sponsor, it results in any of the following outcomes:

- Death,
- A life-threatening adverse event,
- Inpatient hospitalization or prolongation of existing hospitalization,
- A persistent or significant incapacity or substantial disruption of the ability to conduct normal life functions, or
- A congenital anomaly/birth defect
- An important medical event

Life-threatening event: An adverse event or suspected adverse reaction is considered "lifethreatening" if, in the view of either the investigator or sponsor, its occurrence places the patient or subject at immediate risk of death. It does not include an adverse event or suspected adverse reaction that, had it occurred in a more severe form, might have caused death. **Disability** is defined as a substantial disruption in a person's ability to conduct normal life functions. **Hospitalization** for elective treatment of a preexisting condition that did not worsen during the clinical investigation is not considered an AE/SAE. Admittance to an emergency room for observation without being admitted to the hospital may be an AE but is not arbitrarily classified as an SAE. Hospitalization or nursing home admission for the purpose of caregiver respite is not considered an AE/SAE. Complications that occur during hospitalization are AE's, and if a complication prolongs hospitalization, the event is considered serious.

Important medical events that may not result in death, be life-threatening, or require hospitalization may be considered serious when, based upon appropriate medical judgment, they may jeopardize the patient or subject and may require medical or surgical intervention to prevent one of the outcomes listed in this definition. Examples of such medical events include allergic bronchospasm requiring intensive treatment in an emergency room or at home, blood dyscrasias or convulsions that do not result in inpatient hospitalization, or the development of drug dependency or drug abuse.

13.2 Assessment and Grading of AE's/SAE's

13.2.1 Relationship Assessment

For each reported AE, the Investigator must make an assessment of the relationship of the event to study procedures and/or NKA using the following criteria:

- Unrelated: applicable to an AE that occurs when the subject was not exposed to study treatment or another cause is obvious.
- Unlikely to be related: applicable to an AE that meets the following criteria:
 - Does not follow a reasonable temporal sequence from injection of NKA
 - May readily have been produced by the patient's clinical state, environmental, or toxic factors, or other therapy administered to the patient
 - Does not follow a known pattern of response to injection (based on animal data)
- **Possibly related:** applicable to AE's where connection with NKA injection appears unlikely but cannot be ruled out. Applicable to AE's where:
 - It follows a reasonable temporal sequence following injection of NKA
 - It follows a known pattern of response to injection of NKA (based on animal studies)
- **Probably related**: applicable to AE's that are considered, with a high degree of certainty, to be related to NKA. Applicable to AE's where
 - It follows a reasonable temporal sequence from injection of NKA
 - It cannot be reasonably explained by the know characteristics of the patient's clinical state, environmental or toxic factors, or other modes of therapy
 - It follows a known patter of response to NKA injection (based on animal data).

13.2.2 Severity of Adverse Events

All AE's including SAE's will be assessed for severity, using the following grading scale:

Severity of symptoms and abnormal findings will be assessed in this study using the Common Terminology Criteria for Adverse Events (NCI CTCAE, version 4.03).

In the event that an AE is not covered by the NCI-CTCAE grading system, the following definitions will be used:

 \Box Grade 1 - Mild: awareness of sign, symptom, or event, but easily tolerated; does not interfere with usual daily activities or tasks

 $\hfill\square$ Grade 2 - Moderate: discomfort enough to cause interference usual activity and may warrant therapeutic intervention

□ Grade 3 - Severe: incapacitating with inability to perform usual activities and daily tasks; or significantly affects clinical status, ; requires therapeutic intervention

Grade 4 - Life-threatening: immediate risk of death

 \Box Grade 5 - Death

13.3 Recording, Follow-up and Reporting of Adverse Events

13.3.1 Recording of Adverse Events

Subjects will be required to report any AE that occurs after informed consent is signed. All AEs that occurred from the time of informed consent until the 18-month follow-up visit will be recorded with the following precisions.

ICF to Biopsy: Any AE occurring after the patient has signed the ICF but before biopsy should only be recorded on the AE page of the CRF if it is *directly related to study procedures* (e.g., nausea resulting from an agent used for an imaging study). *Any CKD specific event* occurring during this time should be recorded (or updated) on the Medical History page.

Biopsy to Injection: Any AE occurring during or after the biopsy and before injection should be recorded on the AE page only if the event was considered possibly or probably related to the biopsy or other protocol-specified procedure. CKD specific events should be recorded (or updated) on the Medical History page unless, in the opinion of the Investigator, the worsening of the CKD event could be related to the biopsy or other study procedure.

Injection to Month 12 Follow-up: *Any* AE occurring during or after injection until the 12 month follow-up visit should be recorded on the CRF.

Month 12 to Month 18 Follow-up: Following the 12 month visit to the 18 month follow-up visit, *all AE's assessed as product- or procedure-related* should be recorded in the AE CRF. In addition, *any AE's with a severity assessment of "severe" or "life-threatening"* should be recorded in the CRF, regardless of relationship. *Any CKD-related event that meets the definition of an AE* (e.g., clinically significant increase in sCr) should be recorded in the AE CRF. All other AE's do not need to be recorded in the CRF; however, as the PI is responsible for patient safety, the site should record any event that the PI determines should be recorded in the AE CRF.

13.3.2 Recording of Serious Adverse Events

All SAE's should be recorded in the AE CRF from first study procedure through the 6 month follow-up visit. In addition, any SAE's that occur during the long-term observational phase AND are considered related to investigational product, should be recorded in the CRF. All SAE's should be reported according to the procedures discussed below (Section 13.3.4). **13.3.3 Follow-Up of AE's/SAE's**

All AE's that are assessed as related to Investigational Product (i.e., NKA) or study procedures (e.g. biopsy, laparoscopic surgery, or surgical or percutaneous injection) should be followed by the Investigator until the event resolves, stabilizes, or returns to baseline. The investigator should continue to report any significant follow-up information to the Sponsor or Sponsor's designee up to the point the event has been resolved.

SAE's should be followed until the event resolves, stabilizes, or returns to baseline. If the patient insists on discontinuing from the study prior to resolution/stabilization/return to baseline of the SAE, then the patient will continue to be followed as part of the SAE reporting system. That is, the Investigator will continue to follow the patient on a schedule dictated by the clinical situation and submit appropriate follow-up SAE reports as discussed in Section 13.3.4. If the patient refuses to continue to follow-up with the Investigator, then the Investigator may follow the patient through consultation with the patient's primary physician if allowed by the site-approved ICF and applicable regulations.

SAE's that are identified on the last scheduled visit must be recorded in the AE CRF and reported to the Sponsor or Sponsor's designee as outlined in Section 13.3.4. Subjects with unresolved, previously reported serious adverse events, or new serious adverse events identified on the last scheduled visit, should be followed by the investigator until the events are resolved, stabilized, or returned to baseline.

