It is anticipated that all patients will be planned to receive 2 injections under this protocol, in order to allow dose-finding and to understand the duration of effect. Under certain circumstances a patient or investigator may decide to postpone or withhold the second dose. In general, if there appears to be any untoward safety risk, in situations including rapid deterioration of renal function, the development of uncontrolled diabetes, or the development of uncontrolled hypertension, or if there is the intercurrent development of a malignancy, the patient should not receive the second dose.

Second injections under this protocol will be staggered so that single injections in different patients occur no less than 3 weeks apart. The DSMB will review the clinical data regarding each of the first 3 second injections under this protocol, and will consult with the Sponsor before the 2nd, 3rd, and 4th second injections are made. Subsequent second injections will continue to be staggered so as to occur no less than 3 weeks apart, but individual DMSB review will not be required.

No staggering will be required for first NKA injections under this protocol.

Post-Injection Follow-up: Subjects will return to the clinic for follow-up safety assessments on Days 7, 14, and 28 post-injection and at 2, 3, and 6 months post-injection. At 6 months post-injection, post-treatment MRI and renal scintigraphy studies will be conducted. After patients complete the 6 month efficacy visit, they will be considered for a second NKA injection. Patients receiving a second dose will follow the same follow up visits that occurred after first injection. Patients 6 month post first injection visit will serve as the patients 14 to 10 day pre- second injection visit. Patients will return for their second injection and at 2, 3, and 6 months post-injection Patients will be followed up to 18 months in the post follow up phase with 6 months after first NKA injection and 12 months after second NKA injection. Refer to the time and events schedule on page 14 for additional post follow up time points.

Long Term Follow-up: Patients will be followed for safety and efficacy for 24 months after the 18 month initial follow up period. Telephone contact will be made 24 and 36 months after the last NKA injection, and visits will be made at 30 and 42 months after the last NKA injection.

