⁶ Conduct End-of-Study (EOS) assessments at the 18 mo visit, or when the subject discontinues from the study (See Section 6.5). Following the EOS visit, the patient should be rolled into the long-term observational follow-up phase.

⁷ The Chemistry panel includes both standard and renal analytes as described in Table 8. Laboratory assessments are described in detail in Section 12.3.

⁸ A urine pregnancy test should be performed using a urine dip-strip; if positive, then a confirmatory test should be performed by the central laboratory.

⁹ Hemoglobin levels must be verified to be > 9 g/dL within 48 hours of each procedure or per site standard practices for verifying Hb levels prior to an injection or surgical procedure.

¹⁰ On procedure days, HCT and Hb should be measured per site standard practice at the site's local lab so the results are immediately available for clinical care. Samples in lab kits for corresponding visit days should be sent to central laboratory for inclusion in database.

¹¹ Prior to injection, test stick should be performed to confirm absence of signs of infection.

¹² β 2-microglobulin should be assessed in both serum and urine samples.

¹³ Research samples (serum/plasma and urine) will be collected, frozen, and stored for assay of renal specific analytes and/or biomarkers at a future date. Results will not be available for reporting in the CSR for this study.

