11.5 Long term Follow-up

A limited assessment for long term follow-up will continue for 24 months after the initial 18 month follow up period is completed. Telephone contact will be made with patients at 24 months and 36 months after the injection, and patients will be examined at 30 and 42 months after the injection as long term follow up. At the 24 and 36 month visits, urine and blood specimens will be obtained for standard chemistry and renal panel, spot urine, and HbA1c test, an interim physical examination will be conducted, AEs will be reviewed, and the KDQOL will be completed (see Time and Events Schedule).

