11.5.1 Telephone Contact

Patients will be contacted via telephone at 24 and 36 months after the NKA injection in order to inquire about SAEs.

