11.5.2 Visits at 30 and 42 Months

Long term follow-up will extend to 30 and 42 months after the NKA injection and will include a physical exam, CBC, blood chemistries, and KDQOL.

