13 SAFETY ASSESSMENTS AND MANAGEMENT

13.1 Event Definitions

13.1.1 Adverse Events

An Adverse Event (AE) is any untoward medical occurrence associated with the use of a drug or with study participation, regardless of the relationship of the occurrence to study drug or protocol. An AE can be any unfavorable and unintended sign (including an abnormal laboratory finding), symptom or disease temporally associated with the use of the drug, whether or not considered related to the drug. An AE can arise from any use of the drug, and from any route of administration, formulation or dose, including an overdose.

Disease or other specific clinical signs and symptoms which were ongoing prior to study entry (i.e., a "pre-existing" conditions) should be recorded on the Medical History CRF and are not considered AE's unless the condition unexpectedly worsens during the study. Specifically, CKD signs and symptoms which were present at study entry and had been worsening over time are not considered AE's unless there is an unexpected worsening of the events. This would include, for example, an unexpected increase in the rate of disease progression.

Treatment emergent abnormal clinical laboratory findings or other abnormal assessments that are judged by the PI as clinically significant, involve therapeutic medical intervention, or lead to study discontinuation will be recorded as AE's or SAE's if they meet the definition of an AE or SAE presented in this section.

To determine the presence of adverse events, patients should be questioned about the event in a general way, without asking about the occurrence of any specific symptom. The investigator should attempt to establish a diagnosis of the event based on signs, symptoms, and/or other clinical information. In such cases the diagnosis should be documented as the AE and not the individual signs and/or symptoms.

Following questioning and evaluation, all AE's, whether believed by the investigator to be related or unrelated to study procedures and/or NKA, must be documented in the patient's medical records in accordance with the investigator's normal clinical practice and on the AE CRF. Each AE is to be evaluated for nature, duration, severity, seriousness, and causal relationship to NKA administration.

All events will be managed and reported in compliance with all applicable regulations, and included in the final study report.

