14.3 Endpoints

The primary endpoint of the study is to assess the safety and efficacy of NKA injected in one recipient kidney and determine if two injections of NKA provide stabilization of renal function.

- Primary Safety Outcome Measures: procedure and/or product related adverse events (AE's) through 12 months following the initial NKA injection.
- Primary Efficacy Outcome Measures: serial measurement of serum creatinine and estimation of GFR through 6 months following the second cell injection

Secondary Endpoint

The secondary endpoint of the study is to assess the safety and tolerability of NKA administration by assessing renal-specific adverse events over a 12 month period following a patient's first NKA injection.

• Secondary Safety and Tolerability Outcome Measures: renal-specific laboratory assessments through 12 months following the last NKA injection under this protocol, whether first or second.

Exploratory Endpoints

The exploratory endpoint of the study are designed to assess the impact of NKA on renal function over a 12 month period following the initial NKA injection.

• Exploratory Outcome Measures: clinical diagnostic and laboratory assessments of renal structure and function (including eGFR, serum creatinine, and proteinuria) to assess changes in the rate of progression of renal disease; and effect of method of injection on these parameters.

Exploratory quality of life outcome measure will be the Kidney Disease Quality of Life survey obtained at baseline and at 1, 3, 6, 7, 9, 12, 15, 18, 30, and 42 months after a patient's first NKA injection.

- Changes from baseline in BUN, $_{\beta}2$ microglobulin and intact parathyroid hormone (iPTH) at 6 and 12 months post-injection.
- Changes from baseline in C-reactive protein (CRP) at 6 and 12 months post-injection.
- Need for initiation of renal replacement therapy.
- Comparison of pre-injection versus post-injection split functional differences between the left and right kidney based on renal scintigraphy.
- Comparison of pre-injection and post-injection kidney volume estimates based on comparative MRI assessments.
- Subgroup analyses will compare patients receiving a single injection with patients receiving two injections, and patients receiving laparoscopic injections with patients receiving percutaneous injections.

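### From month 18 to 42 the SAE rules require only NKA-related events, so deaths and new malignancies judged unrelated need not reach the CRF, and late renal-replacement starts may be captured inconsistently

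*Combined protocol and SAP*

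**What the plan says.** The synopsis gives the purpose of the late phase: "Patients will be followed for safety and efficacy for 24 months after the 18 month initial follow up period". The laboratory schedule fixes where it starts: "Following the EOS visit, the patient should be rolled into the long-term observational follow-up phase".

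The recording rules for that phase are narrower. Section 13.3.1 sets out AE recording windows, the last of which closes at the 18-month visit. Section 13.3.2 then says that "any SAE's that occur during the long-term observational phase AND are considered related to investigational product, should be recorded in the CRF". Section 13.3.4 requires all SAEs to be reported up to the 18-month visit, and afterwards only those the investigator suspects are product-related.

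Footnote 18 is attached to the AE row of the schedules, which is marked at months 24, 30, 36 and 42. It lists NKA-related SAEs, together with NKA-related AEs and significant CKD-related AEs that the patient reports at the visit.

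Section 11.5.1 describes the calls: "Patients will be contacted via telephone at 24 and 36 months after the NKA injection in order to inquire about SAEs". Section 14.3 lists "Need for initiation of renal replacement therapy" as an exploratory endpoint and gives it no time window.

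**The concern.** In a single-group, open-label study of a new autologous cell product there is no comparator against which a late excess of events would stand out. All-cause recording is what lets an unsuspected signal emerge. A rule that depends on the investigator's attribution removes that safeguard.

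Attribution is also likely to run one way here. Section 13.2.1 ties possible and probable relatedness to a pattern of response known from animal data, and lists the absence of such a pattern under unlikely. Animal follow-up reached at most one year (Section 6.5, Table 2), and Section 13.4.2 expects no product-related events. A harm that first appears after month 18 has no animal pattern to match.

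The renal side is affected too. Section 6 gives delay of dialysis or transplant as the product's purpose. If deaths and renal-replacement starts are not recorded in a uniform way, eGFR at months 30 and 42 is hard to interpret, because Section 14.4.2 imputes nothing and the values come from whoever remains.

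**Working it through.** The plan states no event count or sample size calculation, so there is no figure to reproduce. The check is a comparison of the rules.

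**1. What applies in months 18 to 42**

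| Provision | Requirement | All-cause recording? |
|---|---|---|
| 13.3.1 | Last AE window ends at month 18 | No rule after that |
| 13.3.2 | Record SAEs considered product-related | No |
| 13.3.4 | Report SAEs suspected to be product-related | No |
| Footnote 18 | NKA-related SAEs and AEs; significant CKD-related AEs | For CKD-related AEs only |
| 11.5, 11.5.1 | AEs reviewed; calls ask about SAEs | A question, not a recording rule |
| 13.3.3 | SAEs identified at the last scheduled visit are recorded | Yes, for that visit only |
| 13.6 | Any death halts further injections pending DSMB review | Not a CRF rule |
| 14.7.2 | Treatment-emergent AEs end 18 months post-injection | Summaries stop at the same point |

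**2. Three events traced through the rules**

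- A new malignancy rated unlikely to be related, found before the last visit, is not required by 13.3.2, 13.3.4 or footnote 18.
- A death rated unrelated is not required by any of the three either. It cannot be something the patient reports at a visit.
- A dialysis start reasonably counts as a significant CKD-related AE under footnote 18. Section 13.3.2 does not carry that rule. Section 13.1.1 adds doubt: CKD signs and symptoms present at entry and already worsening "are not considered AE's unless there is an" unexpected worsening.

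**3. The endpoint window**

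Renal replacement is listed under an exploratory objective covering 12 months after the first injection. The same list includes KDQoL at 30 and 42 months, and gives BUN and CRP their own 6- and 12-month time points. Renal replacement has none, so the text does not settle whether it ends at month 12 or month 42.

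**4. Scale**

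- Share of follow-up under the filter: 24 / (18 + 24) = 24/42 = 57%.
- Upper limit of exposure: 30 patients × 2 years = 60 patient-years, if nobody is lost.
- Deaths from any cause over 24 months, for an assumed annual rate r and all 30 entering the phase: p = 1 − (1 − r)², expected number 30p, chance of at least one 1 − (1 − p)^30.

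| r (assumed) | p | Expected deaths | Chance of at least one |
|---|---|---|---|
| 2% | 0.0396 | 1.2 | 0.70 |
| 5% | 0.0975 | 2.9 | 0.95 |
| 10% | 0.19 | 5.7 | 0.998 |
| 16% | 0.2944 | 8.8 | about 1 |

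The 16% row uses the Medicare figure in Section 6.1.2. That figure concerns age 66 and older and has no stated time unit, so it is an upper illustration.

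- Patients crossing eGFR 15 (category G5, Table 1), assuming entry values uniform over 20–50 and a constant loss of r mL/min per year. A crossing between 1.5 and 3.5 years needs an entry value from 15 + 1.5r to 15 + 3.5r.
  - r = 2: range 18–22, overlap with 20–50 is 2/30 = 7%; before month 18, 0%.
  - r = 4: range 21–29, 8/30 = 27%; before, 1/30 = 3%.
  - r = 6: range 24–36, 12/30 = 40%; before, 4/30 = 13%.

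These tables count all events on assumed rates. They do not count unrecorded events. Crossing 15 is also not a dialysis start, and returning patients, who may enter at 15–60, are left out.

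**5. Conflicts in the same sections**

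- 13.3.2 ends all-cause SAE recording at the 6-month visit; 13.3.4 ends all-cause reporting at month 18.
- 11.5 says "At the 24 and 36 month visits, urine and blood specimens will be obtained for standard chemistry and renal panel", and adds an examination, whereas 11.5.1 and the schedules make months 24 and 36 telephone contacts.
- 11.5.2 says that the 30- and 42-month follow-up "will include a physical exam, CBC, blood chemistries, and KDQOL", but the laboratory schedule marks no hematology at those visits.

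**The case against.** The best defence is that the plan captures more than 13.3.2 alone suggests. Section 13.3.2 says what should be recorded and does not forbid more. Section 13.1.1 says in general that AEs go on the CRF whether or not they are related. The calls ask about SAEs without a relatedness filter, any death triggers DSMB review, and early discontinuation after injection is summarised (14.7.1). The CRF itself is not in the documents.

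Much of this stands, and it rules out three stronger readings that a reader might infer.

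- *Dialysis starts are lost.* Not shown. Footnote 18 requires significant CKD-related AEs with no NKA condition at all four late contacts. The exclusion in 13.1.1 covers only expected worsening of signs and symptoms already present at entry, and starting dialysis is a new intervention.
- *The renal-replacement endpoint is undercounted.* This does not follow. If the 12-month objective governs the endpoint, all AEs are recorded over that period. If it runs longer, the defect is an undefined window and capture rule, and no undercount can be calculated.
- *Deaths are invisible.* Too strong. The stopping rule has no relatedness or time limit, and the last-visit rule is all-cause.

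The defence does not supply an all-cause recording rule for the phase. The general sentence in 13.1.1 is narrowed by the windows in 13.3.1. The stopping rule serves decisions about further injections, and the last-visit rule covers one contact. An unrelated death or malignancy between contacts still has no rule that brings it into the database.

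**Conclusion.** The point holds as a gap in the recording rules. For 24 of 42 months, SAE recording and reporting depend on the investigator judging the event NKA-related, so deaths and new malignancies judged unrelated need not enter the CRF. For renal replacement the supportable conclusion is weaker: capture may be inconsistent, because footnote 18 and 13.3.2 differ, the footnote relies on what the patient reports at the visit, and the endpoint has no window.

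The conclusion rests on the text and not on the illustrative rates. They show only that some deaths in this phase are plausible: about 1 to 6 among 30 at assumed rates of 2% to 10% a year. The primary outcomes are not touched, since safety is assessed to 12 months after the first injection and efficacy to 6 months after the second. The change should be made because it is cheap and the late phase has a stated safety purpose.

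**What to change.** - In 13.3.2, 13.3.4, 11.5.1 and footnote 18, require that at each existing month 24, 30, 36 and 42 contact the site records, regardless of relatedness, the date and cause of death, the date of first dialysis or transplant, and any new malignancy. Other SAEs can stay under the present rule.
- State the window of the renal-replacement endpoint: month 42 if the long-term phase is meant to inform it.
- Extend the summaries of death, renal replacement and malignancy past the 18-month limit in 14.7.2.
- Beside any month 30 or 42 eGFR summary, report how many patients had died or started renal replacement, and flag values taken after dialysis began. Dropping those values without the counts would leave a survivors-only summary.
- Reconcile 13.3.2 with 13.3.4 on when all-cause SAE collection ends, 11.5 with 11.5.1 and the schedules on months 24 and 36, and the CBC in 11.5.2 with the laboratory schedule.

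The cost is amendment wording, one short CRF page and a few more late events to enter. The all-cause recording uses contacts already planned and needs no new visit or test.
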